No data on treatment effect and variability based on the CDM1-RS instrument are available; the estimates of mean changes from baseline are not available for placebo, or for the active treatment arm. Three initial scenarios are pre-specified here (treatment effect $\Delta = 5.0, \, \Delta = 3.6, \, \text{and} \, \Delta = 2.1$). However, the clinical relevance of these assumptions is unknown. Additional scenarios will be based on the observed standard deviation and additional assumed treatment differences. Scenarios involving the CGII and/or the Top 3 Caregiver Concerns VAS score may also be assessed. The decisions regarding corresponding sample size increases will be made based on these estimates and other considerations.

Dependent upon the blinded estimate of standard deviation, the sample size may be increased to ensure 80% power for a chosen treatment effect. Any increase in sample size will be limited to 2 times the maximum of the initial sample size. Additional (not pre-specified) scenarios may be requested by the Sponsor after pre-specified scenarios have been reviewed based on various assumptions regarding effect size.

Sample size update due to SSRE

Based on the blinded SSRE, the planned sample size is sufficient to detect the treatment difference between active and control arms based on the primary endpoint with at least 80% power at the 0.05 two-sided significance level. However, the variability of the key secondary endpoint was slightly greater than that originally assumed. Respectively, it was recommended, if operationally feasible, to increase the total sample size to 66 subjects. Further details are in Appendix 2.

As it was not operationally feasible to enroll 66 subjects, 53 subjects were randomized. Sample size calculations based on SSRE results supported this operational decision.

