6.13.1.1 Primary Estimand and Supplementary Analysis

The estimand for the primary efficacy endpoint is the difference between group adjusted means in the changes from baseline in CDM1-RS total score at EOT.

If a subject's in-clinic visit is unavailable, the data will be imputed with the corresponding telehealth assessment. The use of telehealth assessments is thought unlikely to be related to outcome, however, it will be assessed for balance between the treatment groups and sensitivity analyses may be conducted in the event of imbalance.

The null hypothesis being tested for the primary endpoint is that there is no difference in mean change in CDM1-RS total score from baseline to EOT between the tideglusib and placebo treatment groups:

$$H_0$$
: Mean Change_{tideglusib} = Mean Change_{placebo}

The alternative hypothesis is that there is a difference in either direction in the mean change in CDM1-RS total score from baseline to EOT between the tideglusib and placebo treatment groups:

$$H_1$$
: Mean Change_{tideglusib} \neq Mean Change_{placebo}

The analysis will include data from Visit (randomisation) to Visit (EOT) inclusive. Data from other visits will be included in the summaries and listings.

Primary Analysis

The primary estimand will be analysed using a mixed model for repeated measures (MMRM).

The treatment difference between tideglusib and placebo at Visit (EOT) will be estimated as the simple contrast in the treatment effect. The standard error (SE), p-value and 2-sided 95% confidence interval (CI), based on the difference in the Least Squares (LS) means between the two treatment groups will be presented. The LS Means, SE and 95% CI will additionally be presented for each treatment by visit.

The MMRM model will be implemented using restricted maximum likelihood (REML). The Kenward-Roger approximation will be used to estimate the denominator degrees of freedom and standard errors

Initially an unstructured covariance matrix will be investigated. If this analysis fails to converge, the following alternative structures will be tested in the following order until convergence is achieved: Toeplitz, AR(1) and compound symmetry. If a covariance matrix other than unstructured is selected, the estimated standard errors and variance-covariance matrix of the fixed-effects parameters will be computed using a robust "sandwich" estimator (i.e., by specifying the EMPIRICAL option on the PROC MIXED statement).

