The model will contain treatment, age group, visit and treatment by visit interaction as fixed effects, baseline CDM1-RS as a covariate.

If the baseline CDM1-RS and/or age group is not significant at the 15% level (i.e., p>=0.15) then a secondary analysis will be conducted with the term(s) removed from the model. Similarly if the p-value for the treatment by visit interaction is not significant at the 15% level, that term will be removed in the secondary analysis and the LS

Date:22FEB2023 Version: Final 2.0 ST/form/010/15 Means and treatment differences under the assumption of a constant treatment effect over time will be estimated.

Normality of the data will be investigated through plots of the residuals. Non-parametric analyses may additionally be performed if the data are found to be sufficiently non-normal. This will include non-parametric analysis of covariance (ANCOVA) (Koch G.G. et al, 1998 and Zink, R. and Koch, G.G., 2012) of the change from baseline to Visit with treatment, baseline CDM1-RS and age group as covariates.

Any data collected after study discontinuation will not contribute to the treatment effect estimate. Only data up to study discontinuation will be used.

Missing Data

Missing data due to early study discontinuations or missed visits are assumed to be missing at random (MAR) and observed data only will be used for the primary analysis. The MMRM accounts for these missing data using a direct likelihood approach.

Sensitivity Analysis

Several sensitivity analyses will be applied to this endpoint:

Sensitivity analysis 1 – Multiple Imputation: Missing at Random (MAR)

At a visit, if a subject has no in-clinic or telehealth assessment data the visit is assumed to be MAR. This assumes that subjects with missing data follow the same trajectory as other subjects in their respective treatment arm that have complete data.

- Intermittent missing data will first be imputed using the MCMC method, appropriate for non-monotonic missing data.
- Data missing after subjects discontinue the study early will be imputed using a regression, appropriate for monotone missingness. At each time point, missing data will be assumed to follow a distribution similar to scores for subjects who are still in the study and randomized to the same treatment group.

The MI method (as described in Section 6.3) will be employed with the following assumptions/steps:

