- Covariates that may be used in the MI will include treatment group, age group and baseline CDM1-RS.
- 20 imputations will be completed.
- Seed number and covariates used for imputation will be agreed prior to data base lock and detailed in the TFL outputs.

The MMRM will be applied to each of the multiply imputed data sets, as described above for the primary estimand. The estimates from these models will then be combined using Ruben's (1987) rule and analysed to provide the endpoint estimates and summarized.

Sensitivity analysis 2 – Single Imputation: WOCF

At a visit, if a subject has no in-clinic or telehealth assessment data the visit is assumed to be MAR. This assumes that the trajectory of subjects who discontinue the study follows that of their worst observation. Worst Observation Carried Forward (WOCF)

will be used and the MMRM as described above for the primary estimand will be applied to these data.

Sensitivity analysis 3 – Multiple Imputation: In-clinic visits only

At a visit, if a subject has a telehealth assessment and no in-clinic assessment the visit is assumed to be MAR. Modelling in-clinic visits only (sensitivity analysis 3) is deemed a more valuable analysis than modelling telehealth visits only (sensitivity analysis 4).

- Intermittent missing data for in-clinic visits will first be imputed using the MCMC method, appropriate for non-monotonic missing data.
- Data missing after subjects discontinue the study early will be imputed using a regression, appropriate for monotone missingness. At each time point, missing data will be assumed to follow a distribution similar to scores for subjects who are still in the study and randomized to the same treatment group.

The MI procedure will be employed as described for sensitivity analysis 1. The MMRM will be applied to the multiply imputed data sets, as described above for the primary estimand. The estimates from these models will then be combined using Ruben's (1987) rule and analysed to provide the endpoint estimates and summarized.

Sensitivity analysis 4 – Multiple Imputation: Telehealth visits only

At a visit, if a subject has an in-clinic assessment and no telehealth assessment the visit is assumed to be MAR.

- Intermittent missing data for telehealth visits will first be imputed using the MCMC method, appropriate for non-monotonic missing data.
- Data missing after subjects discontinue the study early will be imputed using a

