- 3. Seed number and covariates used for imputation will be agreed prior to data base lock and detailed in the TFL outputs.

The MMRM will be applied to each of the multiply imputed data sets, as described above for the key secondary estimand. The estimates from these models will then be combined using Ruben's (1987) rule and analysed to provide the endpoint estimates and summarized.

Sensitivity analysis 2 – Single Imputation: WOCF

At a visit, if a subject has no in-clinic or telehealth assessment data the visit is assumed to be MAR. This assumes that the trajectory of subjects who discontinue the study follows that of their worst observation. WOCF will be used and the MMRM as described for the key secondary estimand and applied to these data.

Sensitivity analysis 3 - Multiple Imputation: In-clinic visits only

At a visit, if a subject has a telehealth assessment and no in-clinic assessment, the visit is assumed to be MAR. Modelling in-clinic visits only (sensitivity analysis 3) is deemed a more valuable analysis than modelling telehealth visits only (sensitivity analysis 4).

- Intermittent missing data for in-clinic visits will first be imputed using the MCMC method, appropriate for non-monotonic missing data.
- Data missing after subjects discontinue the study early will be imputed using a regression, appropriate for monotone missingness. At each time point, missing data will be assumed to follow a distribution similar to scores for subjects who are still in the study and randomized to the same treatment group.

The MI procedure will be employed as described for sensitivity analysis 1. The MMRM will be applied to the multiply imputed data sets, as described for the key secondary estimand. The estimates from these models will then be combined using Ruben's (1987) rule and analysed to provide the endpoint estimates and summarized.

Sensitivity analysis 4 – Multiple Imputation: Telehealth visits only

At a visit, if a subject has an in-clinic assessment and no telehealth assessment, the visit is assumed to be MAR.

- Intermittent missing data for telehealth visits will first be imputed using the MCMC method, appropriate for non-monotonic missing data.

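### The multiple-imputation sensitivity analyses are pooled by the 1987 rule with no small-sample degrees of freedom, so they use a slightly more liberal reference than the Kenward-Roger primary (intervals about 3% shorter than under Barnard-Rubin)

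*SAP*

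**What the plan says.** SAP 6.13.1.1 analyses CDM1-RS with a REML-based MMRM and gives it small-sample inference: "The Kenward-Roger approximation will be used to estimate the denominator degrees of freedom and standard errors". SAP 6.13.2.1 does the same for CGI-I. If the unstructured covariance does not converge, both sections fall back to simpler structures with sandwich standard errors. Neither section says which df go with those.

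The imputation plan is set under sensitivity analysis 1 in 6.13.1.1: "20 imputations will be completed", and then "The MMRM will be applied to each of the multiply imputed data sets, as described above for the primary estimand". Pooling follows the 1987 rule of Rubin (spelled Ruben in the text): "The estimates from these models will then be combined using Ruben's (1987) rule". Analyses 3, 4, 7 and 8 refer back to analysis 1 and repeat the pooling statement. The CGI-I set uses the same words: "combined using Ruben's (1987) rule and analysed to provide the endpoint estimates".

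SAP 6.3 describes multiple imputation in general terms and says only that the estimates are combined. Neither document names a pooled df, a complete-data df or a small-sample adjustment, and neither rules one out.

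Two other provisions matter. Analysis 8 looks for a tipping point, defined as the adjustment at which significance is lost. SAP 6.14 ties any key secondary claim to the primary analysis and treats supportive analyses as supportive only.

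**The concern.** The 1987 rule carries its own df formula, derived as if the complete-data analysis had unlimited df. In a large trial this does not matter. With 53 children the complete-data analysis has roughly 40 to 50 df, so read literally the rule gives a pooled test close to a z-test, while the primary uses a t-test with finite df.

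That is the wrong direction for a robustness check. Analysis 1 shares the primary's missing-at-random assumption, so a difference between the two in significance could come from the df alone. In analysis 8, a smaller critical value means significance is lost at a larger adjustment, which makes the result look a little more robust than it is. The gap also widens with missing information. It could therefore be larger in analyses 3 and 4, which treat one mode of assessment as missing.

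**Working it through.** **Inputs**
- Imputations: m = 20 (SAP 6.13.1.1).
- Sample: "As it was not operationally feasible to enroll 66 subjects, 53 subjects were randomized" (SAP 3).
- Model: "The model will contain treatment, age group, visit and treatment by visit interaction as fixed effects, baseline CDM1-RS as a covariate" (SAP 6.13.1.1). For the end-of-treatment contrast I count the intercept, treatment, age group and baseline, so the complete-data df are v = 53 - 4 = 49. This assumes two age groups (the levels are redacted) and all 53 children in the ITT set. I use 40 to 49 as the range.
- Share of variance due to missing data, g: not in the documents. I take 0.10-0.13, guided by the planned 10-13% dropout, and show 0 to 0.5.
- SD 2.64, difference 2.2 and 25 per group (Protocol 11.1).

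**Plan's own figure.** The documents give no df, interval or p-value for the pooled analyses. The nearest figure is the 82% power in Protocol 11.1. A noncentral-t calculation gives 82.3%, so it reproduces. The matching unadjusted SE is 2.64 × √(2/25) = 0.747.

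**Degrees of freedom**
- 1987 rule: df = (m - 1)/g².
- Barnard-Rubin: df = 1/(1/df1987 + 1/dfobs), where dfobs = [(v + 1)/(v + 3)] × v × (1 - g).

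For g = 0.10 and v = 49, the 1987 rule gives 19/0.01 = 1,900. Then dfobs = (50/52) × 49 × 0.90 = 42.4, and Barnard-Rubin gives 1/(1/1,900 + 1/42.4) = 41.5.

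| v | g | df 1987 | df B-R | t 1987 | t B-R | 1987 interval shorter by | 1987 p when B-R p = 0.050 |
|---|---|---|---|---|---|---|---|
| 49 | near 0 | very large | 47.1 | 1.960 | 2.012 | 2.6% | 0.044 |
| 49 | 0.10 | 1,900 | 41.5 | 1.961 | 2.019 | 2.9% | 0.044 |
| 49 | 0.13 | 1,124 | 39.5 | 1.962 | 2.022 | 3.0% | 0.043 |
| 49 | 0.30 | 211 | 28.5 | 1.971 | 2.047 | 3.7% | 0.042 |
| 49 | 0.50 | 76 | 18.0 | 1.992 | 2.101 | 5.2% | 0.039 |
| 40 | 0.10 | 1,900 | 33.7 | 1.961 | 2.033 | 3.5% | 0.042 |
| 40 | 0.13 | 1,124 | 32.2 | 1.962 | 2.036 | 3.6% | 0.042 |
| 40 | 0.50 | 76 | 15.2 | 1.992 | 2.128 | 6.4% | 0.037 |

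The primary with 49 df uses t = 2.010. The limit of no missing data shows the flaw most plainly. Estimate and SE are then the same as in the complete-data analysis, but the statistic is compared with 1.960, and the size is 2 × P(t with 49 df > 1.960) = 5.6%.

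**In scale points.** 0.747 × (2.019 - 1.961) = 0.04 points of half-width, on a scale of 0 to 44 (11 items scored 0-4).

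**Simulated size.** The stand-in for the trial had 53 children, monotone dropout, 20 regression imputations and a covariate-adjusted end-of-treatment contrast in place of the MMRM. The SAP lists treatment among the possible imputation covariates and also describes same-arm imputation, so both were looked at.
- Treatment as covariate, 13% dropout, 24,000 null trials (Monte Carlo SE 0.14 points): 5.2% with 1987 df, 4.7% with Barnard-Rubin.
- Treatment as covariate, 4,000 trials each (SE 0.34 points): 5.0% against 4.5% at 10% dropout, and 5.0% against 4.3% at 25%.
- Treatment as covariate, separate simulation at 6-12% dropout: 5.4-5.5% against about 4.8%.
- By arm, 1987 df: 5.25%, 4.9% and 4.2% at 6%, 12% and 25% dropout. Another by-arm run (9,000 trials per setting) gave 5.4% at 6% and 5.7% at 12%. The 5.7% was not reproduced and I do not rely on it.
- Control-based (the type of analysis 7), 1987 df: 3.9%, 3.1% and 1.4% at 10%, 13% and 25% dropout.

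**The case against.** The case against acting is strong on size. The SAP is silent on pooled df rather than opposed to a small-sample version. Kenward-Roger standard errors stay in the within-imputation variance, so only the df are at issue. Barnard-Rubin is not exact either: its 4.7% in the largest simulation lies about two Monte Carlo standard errors below 5%. A change of 0.04 points against a planned difference of 2.2 is clinically negligible. The tipping-point search runs only after a significant result, and its shift has not been quantified.

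Most of this stands and sets the grade. It does not remove the point. The only pooling instruction in the SAP is a named rule whose df ignore the sample size, and two programmers working from that text could report different p-values.

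A reader might infer more: that every imputation analysis has intervals that are too narrow and an inflated error rate, or that a favourable analysis 1 could rescue a failed primary. The documents and the checks do not support this. Control-based analysis 7 is conservative even with the 1987 df, by-arm imputation shows no inflation at about 12% dropout or more, and SAP 6.14 lets only the primary analysis open the key secondary claim. Nor should the 5.6% be read as the operating size of these analyses. It takes the finite-df t as the exact reference and applies in the limit of no missing data.

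**Conclusion.** The point holds as a minor one. Against the small-sample rule, the 1987 rule shortens intervals by about 3% at the planned dropout (2.6% to 6.4% over the full range examined). It gives analysis 1 a slightly more liberal reference than the primary under the same assumption, and moves the tipping point of analysis 8 slightly outward. Type I error inflation is at most about half a percentage point, at low missingness with treatment as an imputation covariate.

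Primary and key secondary inference does not change, because both rest on the direct-likelihood MMRM.

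The result depends on assumed complete-data df of 40 to 49, on missing information of similar size to the dropout rate, and on simulations that used a covariate-adjusted contrast with an illustrative visit number and correlation.

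**What to change.** Add one sentence to SAP 6.3 and refer to it in 6.13.1.1 and 6.13.2.1: pooled inference uses the Barnard-Rubin small-sample df (the EDF option in the SAS pooling step), with the complete-data df taken from the end-of-treatment treatment contrast of the fitted MMRM. Under the unstructured covariance this is the Kenward-Roger df. For the sandwich fallback, name the df to be used. Because the Kenward-Roger df can differ slightly between imputed data sets, say also how one value is chosen. Apply the rule to analyses 1, 3, 4, 7 and 8 for both endpoints, including every step of the tipping-point search.

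The cost is one sentence and one program option. Intervals become about 3% wider, and analyses where Rubin's variance is already conservative, such as analysis 7, become slightly more so. If the analyses have already been run, only the pooling step needs repeating, and the report should state which df were used.

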6.12 COVID-19 Impact to study

Due to the global COVID-19 (Coronavirus Disease 2019) pandemic and the potential for resurgences of COVID-19, for the purposes of this protocol, 'in-clinic' visits, when pertaining to Visits -Visit (Weeks), may be conducted via a combination of telehealth and home healthcare providers for COVID-19 related reasons e.g. institutional restrictions, travel restrictions, quarantine or shielding prevent subjects from being seen in-person at the investigator site.

Subjects who have completed Screening (Visit but are unable to attend Run-In (Visit in-person due to COVID-19 related reasons will be allowed the opportunity to rescreen for the study if study enrolment is still ongoing once they are able to attend the clinic again in person. These subjects will have a new screening number and will be treated as a separate subject in the tables and listings. Subjects who have attended the Run-In (Visit and are unable to attend the Baseline (Visit in-person due to COVID-19 related reasons will be discontinued and replaced.

All subjects are expected to have an in-clinic visit for all pre-specified timepoints (except for the collection of AE and concomitant medication data at Visits and Should an in-clinic visit be missed the corresponding telehealth visit and/or home health care visit can replace it. Additionally, there will be 3 occasions in the study (Visit and Visit and Visit where dual telehealth and in-clinic assessments will be conducted. To evaluate the consistency of telehealth data and in-clinic data for the CDM1-RS and CGI rating scales and to minimize the potential bias, Visits and are performed using both in-clinic and telehealth data collection approaches. Sensitivity analyses to evaluate the consistency of these two methods of data collection is provided in sections 6.13.1 and 6.13.2.

It is noted that particular attention may need to be given to the impact on key efficacy or safety assessments as a result of the COVID-19 pandemic. Consideration of the different areas of impact has been made as described below:

- Important protocol deviations related to COVID-19 will be recorded under the
 deviation category of 'Other' with a free text reason indicating the deviation was
 due to COVID-19. The assigned categories will be presented in the protocol
 deviation listing and table summary of important deviations as described in
 section 6.7.

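### Sensitivity analysis 4 should be limited to the planned dual-rating visits; at any other visit telehealth is absent by design and the imputation has little or no telehealth data to draw on

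*SAP*

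**What the plan says.** **Where telehealth is planned.** SAP 6.12 makes the clinic the default mode: "All subjects are expected to have an in-clinic visit for all pre-specified timepoints". It then says that "there will be 3 occasions in the study" with both a telehealth and an in-clinic rating. Protocol 10.1.1.1 and 11.5 identify these as Baseline and two later visits. At any other rating visit, Protocol 10.1.1.1 (CDM1-RS) and 10.1.1.2 (CGI) allow telehealth only in place of a clinic interview that COVID-19 prevents.

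**What sensitivity analysis 4 does.** For the CDM1-RS, SAP 6.13.1.1 says that "if a subject has an in-clinic assessment and no telehealth assessment the visit is assumed to be MAR". The next step is: "Intermittent missing data for telehealth visits will first be imputed using the MCMC method, appropriate for non-monotonic missing data". Regression imputation follows after discontinuation, then the primary MMRM, which takes data from randomisation to end of treatment (EOT). The number of imputations is carried over from sensitivity analysis 1: "20 imputations will be completed". For the CGI-I, SAP 6.13.2.1 repeats the rule: "if a subject has an in-clinic assessment and no telehealth assessment, the visit is assumed to be MAR". Neither paragraph limits the analysis to the dual-rating visits.

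**The concern.** The rule mirrors that of sensitivity analysis 3, the in-clinic-only version. There it works: the clinic is the planned mode at every visit, so a gap is an exception. For telehealth the position is reversed. At a visit without a planned telehealth rating, an empty cell is the norm and a value is the exception, yet the rule sends every such cell to the imputation step.

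The trouble is one of estimation. To draw a value for a visit, the MCMC model needs that visit's mean, variance and covariances with the other visits. With few or no observed telehealth scores there, the procedure may not run, or its draws may reflect the prior. The few scores that do exist come from children whose clinic visit was prevented.

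Three parts of the output are exposed:

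- the telehealth least squares means, which the MMRM reports for each arm at each visit;
- any constant-effect version, if the secondary model that drops a non-significant treatment-by-visit term is carried into this analysis, because imputed interim values would then enter the treatment estimate directly;
- whether the analysis can be run as specified.

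**Working it through.** The plan gives no figure for the imputed share, so there is none to reproduce. The check is a count.

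**Inputs**

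- Planned telehealth occasions: 3, of which 2 are after baseline (SAP 6.12; Protocol 10.1.1.1, 11.5).
- Randomised: 53 (SAP 3).
- Interim CDM1-RS rating visits between Baseline and EOT, *k*: redacted. Protocol Table 1 has seven interim columns, so *k* is at most 7.
- Interim visits that are dual-rated, *d*. The central rater scores recordings at Baseline and the two later dual visits only (Protocol 10.1.1.1; SAP 6.13.3.4), yet the central-rater endpoints are defined at EOT (Protocol 11.5; SAP 2.3). EOT therefore appears to be one of the two, giving *d* = 1. If it is not, *d* = 2.
- COVID-19 substitution rate at a visit without planned telehealth, *c*: not given. Assumed range 0% to 30%.

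**Step 1: telehealth scores available at such a visit.** Expected number, both arms together and ignoring dropout, is 53 × *c*:

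- 0%: 0
- 5%: 53 × 0.05 = 2.65, about 3
- 10%: 53 × 0.10 = 5.3, about 5
- 20%: 53 × 0.20 = 10.6, about 11

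Compare this with what must be estimated. Regressing the CDM1-RS telehealth score at that visit on treatment, age group, baseline and the two planned post-baseline telehealth scores needs an intercept plus 5 slopes, or 6 coefficients (counting one for age group, the minimum), before the residual variance. At 10% there are fewer scores than coefficients. At 0% nothing about the visit can be estimated from telehealth data.

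The covariates that SAP 6.13.1.1 lists as possible for the imputation are treatment, age group and baseline CDM1-RS; SAP 6.13.2.1 lists only treatment and age group. The same child's in-clinic score at the same visit, which is observed whenever the rule applies, is in neither list.

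**Step 2: share of interim telehealth cells empty by design.** Share = (*k* − *d*)(1 − *c*) / *k*, ignoring dropout.

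| *k* | *d*=1, *c*=0 | *d*=1, *c*=20% | *d*=1, *c*=30% | *d*=2, *c*=0 |
|---|---|---|---|---|
| 1 | 0% | 0% | 0% | – |
| 2 | 50% | 40% | 35% | 0% |
| 3 | 67% | 53% | 47% | 33% |
| 5 | 80% | 64% | 56% | 60% |
| 7 | 86% | 69% | 60% | 71% |

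Example: *k* = 5, *d* = 1, *c* = 20% gives (5 − 1) × 0.80 / 5 = 64%. The range runs from 0% to 86%, and the documents do not say where in it the trial lies.

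**Step 3: reach into the EOT contrast.** With *d* = 1, telehealth baseline and telehealth EOT are both scheduled. For a child with both observed, the EOT contrast uses those scores. Imputed interim values then act mainly through children who drop out and through the common baseline slope.

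**Step 4: after restriction to the three dual-rating visits.** The share imputed because telehealth was never scheduled is 0%. Only missed ratings and dropout remain.

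**The case against.** The strongest reply is that the wording can be read more narrowly. The analysis is headed as telehealth visits only, and its imputation step speaks of gaps in telehealth visits, which could mean the scheduled telehealth series. The imputation covariates are also to be settled before database lock. But the sentence that defines a missing visit turns on an in-clinic rating being present and a telehealth one absent, at any visit. A programmer following it would impute the unscheduled visits too.

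It is also fair that the analysis carries little weight. It is one of eight sensitivity analyses on each endpoint, and the SAP ranks it below analysis 3. Agreement between modes is examined separately at the dual visits through paired differences, correlations and plots. This limits the importance of the point but does not remove it.

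A reader might infer four stronger things, none of which the documents support:

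- *That MAR is wrong here.* A rating absent by design is missing for a reason unrelated to outcome, which satisfies MAR.
- *That most of the telehealth data would be imputed.* This depends on the redacted rating schedule. The choice of fallback covariance structures for the CDM1-RS (Toeplitz, AR(1), compound symmetry) hints at three or more post-baseline visits, since the three coincide with two, but that is only a hint.
- *That the EOT result would rest mainly on imputed values.* Step 3 points the other way.
- *That 20 imputations are too few.* What matters is the missing information for the EOT contrast, not the count of empty interim cells, and the documents do not allow it to be calculated.

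**Conclusion.** The point holds as a specification fault in a supporting analysis, for both the CDM1-RS and the CGI-I. As written, the rule imputes telehealth scores at every modelled visit with a clinic rating and no telehealth rating, although telehealth is planned at only three occasions. At any other rating visit the imputation has few or no telehealth scores behind it, so by-visit telehealth means and any constant-effect estimate would rest on imputed values there.

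The size is small. The number of affected visits cannot be determined; it is zero if the scale is rated only at the dual visits. The EOT contrast would be affected only modestly, on the inference that EOT is dual-rated. The primary and key secondary analyses are unaffected. The counts of available scores rest on assumed substitution rates.

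**What to change.** In the sensitivity analysis 4 paragraphs of both SAP 6.13.1.1 and SAP 6.13.2.1:

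- name the visits covered: the telehealth baseline and the two planned post-baseline telehealth occasions;
- fit the MMRM to those visits only;
- impute only telehealth ratings that were scheduled at those visits but not done, including those lost to dropout.

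The cost is a few sentences of SAP text, with less programming than the present wording requires. The one real loss is that the few COVID-19 substitute ratings at other visits drop out of this analysis. They remain in the primary analysis and can be listed.
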